5.5.3 Concomitant treatments

Other medication other than that described above, which is considered necessary for the patient's safety and well-being, may be given at the discretion of the Investigator and recorded in the appropriate sections of the Case Report Form. In addition, any unplanned diagnostic, therapeutic or surgical procedure performed during the study period must be recorded in the CRF. Patients must comply with the concomitant treatment information described in the core study protocol and those described in the olaparib Investigators' Brochure.

5.5.3.1 Women of childbearing potential

Women of childbearing potential (WoCBP) may be included only if acceptable contraception is in place for 2 weeks before commencing study treatment for the duration of the study, and for 1 month after the last dose of study drug. Women of childbearing potential and their partners, who are sexually active, must agree to the use of TWO highly effective forms of contraception in combination (see [Appendix G Definition of Childbearing Potential and Acceptable Contraceptive Methods](#)), throughout the period of taking study treatment and for at least 1 month after last dose of study drug(s), or they must totally/truly abstain from any form of sexual intercourse. Contraceptives that are prone to drug-drug interactions may not be effective due to a potential CYP3A4 interaction with ceralasertib.

All WoCBP must have a negative pregnancy test during screening and within 3 days prior to starting each treatment cycle.

Male patients who are involved in the study must agree to avoid procreative and unprotected sex (ie, using acceptable forms of contraception as described in [Appendix G](#)) and must not donate sperm during the study and for 6 months after the last dose of study drug. Where the female partner is pregnant or not using effective birth control, men should be advised to abstain while in the study and for 6 months after the last dose of study drug.

Female partners, who are of childbearing potential, of men participating in the study will also be required to use effective contraceptive measures (detailed in [Appendix G](#)) while their partner is on study drug and for 6 months thereafter.

5.5.4 Photosensitivity

Patients are advised to take precautions when outside in the sun, e.g., limiting the duration of sun exposure, wearing protective clothing (hat and sunglasses) and sunscreen

5.6 Discontinuation of investigational product

See Section [4.9](#) of the master protocol.

5.7 Criteria for withdrawal

See Section [4.10](#) of the master protocol.

5.8 Discontinuation of the study

See Section [4.11](#) of the master protocol.

6. STUDY PLAN AND TIMING OF PROCEDURES

The procedures for the screening and the treatment periods in this study are presented in [Appendix C Table 3 Schedule of assessment for olaparib + ceralasertib \(AZD6738\) combination therapy](#)

Appendix C Table 3 Schedule of assessment for olaparib + ceralasertib (AZD6738) combination therapy

		Screening	Cycle 1			Subsequent on treatment visits (every 28 days)	Study treatment discontinued	30-day follow-up after last dose of study medication	Follow up for progression and survival	Details in section
			2	3	4					
Visit Number			2	3	4	Visit No.5 onwards				
Day		-28 to -1	1	7	15	Cycle X, Day 1			Every 8 weeks ⁿ	
Visit Window					± 3d	up to 3 days prior to CXD1	up to 7 days after discontinuation	± 7d	± 7d	
Informed consent		X								Appendix C section 6.1
Optional Informed consent for Optional exploratory genetic sample		X								Appendix C section 7.4.5
Optional Informed consent for Tumor Biopsy		X								Appendix C section 6.1
Medical / surgical history ^a		X								Appendix C section 6.1
Demographics		X								Appendix C section 6.1
Smoking consumption		X								Appendix C section 6.1
Inclusion/ Exclusion criteria		X								Appendix C sections 5.1 and 5.2
Concomitant medications including blood transfusions		X	X	X	X	X	X	X		Section 8.7 of master protocol and Appendix C sections 5.5 and 9.7

		Screening	Cycle 1			Subsequent on treatment visits (every 28 days)	Study treatment discontinued	30-day follow-up after last dose of study medication	Follow up for progression and survival	Details in section
			2	3	4					
Visit Number			2	3	4	Visit No.5 onwards				
Day		-28 to -1	1	7	15	Cycle X, Day 1			Every 8 weeks ⁿ	
Visit Window					± 3d	up to 3 days prior to CXD1	up to 7 days after discontinuation	± 7d	± 7d	
Adverse events ^b		X	X	X	X	X	X	X		Section 7 of master protocol and Appendix C section 8
Vital signs (BP, pulse and temperature)		X	X			X	X	X		Section 6.2.4 of master protocol and Appendix C section 7.1.2
Physical examination and weight ^c		X	X			X	X	X		Section 6.2.2 of master protocol and Appendix C section 7.1.1
ECOG performance status		X	X			X	X			Section 6.3.1 of master protocol and Appendix C section 7.1.1
Pregnancy test ^d		X	X			X		X		Section 6.2.1 of master protocol
Triplicate ECG ^e		X	X	X		X	X			Section 6.2.3 of master protocol and Appendix C section 7.1.3
Haematology, coagulation, chemistry and urinalysis ^f		X	X	X	X	X ^f	X	X		Section 7.1.4 of Appendix C

		Screening	Cycle 1			Subsequent on treatment visits (every 28 days)	Study treatment discontinued	30-day follow-up after last dose of study medication	Follow up for progression and survival	Details in section
			2	3	4					
Visit Number			2	3	4	Visit No.5 onwards				
Day		-28 to -1	1	7	15	Cycle X, Day 1			Every 8 weeks ⁿ	
Visit Window					± 3d	up to 3 days prior to CXD1	up to 7 days after discontinuation	± 7d	± 7d	
Hepatitis B, C and HIV		X								Section 6.3.2. of master protocol
Blood sample for Cytokines			X	X	X	X	X ^m			Section 7.4.1 and 7.4.2 of Appendix C
PK analysis ^g			X	X		Cycles 2 to 6 only				Section 6.4 of master protocol and Appendix C section 7.2
Blood samples for biomarker analysis: plasma and PBMCs isolated from whole blood			X	X	X	X	X ^m			Section 6.6 of master protocol
Peripheral blood for CCI			X			X	X ^m			Section 6.6.1.3 of master protocol and Appendix C section 7.4.1
Peripheral blood for CCI			X		X		X ^m			Sections 6.6.1.2 and 6.6.1.3 of master protocol and Appendix C section 7.4.2
mRNA			X							Appendix C section 7.4.1

		Screening	Cycle 1			Subsequent on treatment visits (every 28 days)	Study treatment discontinued	30-day follow-up after last dose of study medication	Follow up for progression and survival	Details in section	
			2	3	4						
Visit Number			2	3	4	Visit No.5 onwards					
Day		-28 to -1	1	7	15	Cycle X, Day 1			Every 8 weeks ⁿ		
Visit Window					± 3d	up to 3 days prior to CXD1	up to 7 days after discontinuation	± 7d	± 7d		
Tumour assessment (RECIST 1.1) ^h		X	First scan at 8 weeks, then 4 weeks later (i.e. at 12 weeks) and then every 8 weeks (all ± 1 week), from the first day of investigational drug administration for the first 72 weeks, then every 12 weeks ± 1 week hereafter, until disease progression.								Section 6.1 of master protocol
Archival tissue (if available) ⁱ		X								Appendix C Section 7.4.3	
Tumour biopsy with biomarker analyses (optional) ^j		X		X			X ^m			Appendix C Section 7.4.4	
Optional exploratory genetic sample (optional)		X								Appendix C Section 7.4.5	
Ceralasertib and olaparib dispensing			X			X				Appendix C Section 9	
Dispense/review/collect Dosing Diary ^k			X	X	X	X				Appendix C Section 9	
Dosing with ceralasertib ^l			Dosing once daily on Days 1-7 only								Appendix C sections 9.1.1. and 9.2
Dosing with olaparib ^l			Continuous twice daily dosing								Appendix C sections 9.1.2 and 9.2
Post discontinuation anticancer therapy ^o									X	NA	

		Screening	Cycle 1			Subsequent on treatment visits (every 28 days)	Study treatment discontinued	30-day follow-up after last dose of study medication	Follow up for progression and survival	Details in section
Visit Number			2	3	4	Visit No.5 onwards				
Day		-28 to -1	1	7	15	Cycle X, Day 1			Every 8 weeks ⁿ	
Visit Window					± 3d	up to 3 days prior to CXD1	up to 7 days after discontinuation	± 7d	± 7d	
Survival status									X	Section 6.1.1 of master protocol

- a This should include any previous cancer therapies (including radiotherapy and respond to current chemotherapy regimen) as well as any history of blood transfusion 120 days prior to entry to the study, with reasons (e.g. bleeding or myelosuppression).
- b All ongoing AEs/ SAEs and any new AEs / SAEs identified during the 30 calendar day’s follow-up period after last dose of study medication must be followed up to resolution.
- c Physical examination should be done as per schedule but does not need to be recorded in the eCRF after the baseline assessment (except for weight which should be collected at each visit). Any clinically significant changes not unequivocally related to disease progression should be recorded as AEs. Height will be measured at screening only.
- d Pregnancy tests using blood or urine samples will be performed for women of childbearing potential within 28 days prior to the start of study treatment, on Day 1 of the study prior to commencing treatment, on Day 1 of each subsequent cycle and at the follow-up visit 30 days after last dose of study medication. If results are positive, the patient must be discontinued from the study treatment immediately. Tests will be performed by the hospital’s local laboratory.
- e Triplicate ECG is required within 7 days prior to starting study treatment. All ECG assessments to be done in triplicate pre-dose on Cycle 1 Day 1 (additional baseline), within 1-2 hours of dosing on Day 7 of cycle 1, and Day 1 of every subsequent cycle, and on discontinuation of study treatment.
- f Lab tests include FBC, Coagulation, Clinical Chemistry, CRP, urinalysis (coagulation test and urinalysis should be performed at screening and only if clinically indicated thereafter). Safety blood samples should be assessed prior to starting a new cycle, ideally on the day dosing is planned, but within 3 days prior to dosing will be acceptable.
- g A common PK time window will be used for olaparib and ceralasertib in all patients: Cycle 1 Day 1: 1-3 hours, 3-6 hours and 6-12 hours post-dosing, Cycle 1 Day 7: pre-dose, 0.5-1 hour, 1-3 hours, 3-6 hours and 6-12 hours post-dosing, and Cycle X Day 1: single sample at 1-6 hours post-dosing only
- h RECIST 1.1 assessments will be performed on images from CT (preferred) or MRI, each preferably with IV contrast of the chest, abdomen (including liver and adrenal glands), and pelvis. Pelvic imaging is recommended only when primary or metastatic disease in the pelvic region is likely. Additional anatomy should be imaged based on signs and symptoms of individual patients at baseline and follow-up. Baseline assessments should be performed no more than 28 days before the date of enrollment and, ideally, should be performed as close as possible to and prior to the start of the initial dose of IP. If an unscheduled assessment was performed and the patient has not progressed, every attempt should be made to perform the subsequent assessments at their next scheduled visit.
- i Archival tissue collection if available, ideally 10 x 5 µm sections for sequencing
- j Optional biopsy can be taken in Cycle 1 between day 3 and day 8, up to 24 hours after the last dose of ceralasertib in that cycle. At study treatment discontinuation, the biopsy can be taken between 0 and 96 hrs post last dose.
- k Review ceralasertib and olaparib dosing compliance with the patient at the beginning of each new treatment cycle when study drug is dispensed.
- l Ceralasertib should be taken with approximately 8 ounces of water. When ceralasertib is administered in combination with olaparib, patients must fast for at least 2 hours prior to the dosing and for at least 1 hour after the dose. When olaparib is given on its own, the olaparib tablet formulation can be given without regard to food. Please note that the cycle length for ceralasertib + olaparib and olaparib monotherapy will be 28 days.

Clinical Study Protocol Appendix C

Drug Substance Durvalumab (MEDI4736), tremelimumab, AZD1775, carboplatin, olaparib, ceralasertib (AZD6738)

Study Code D419QC00002

Version 05

Date 16Jan2020

m Progression only

n Following treatment discontinuation, assessments for survival must be made monthly for the first 3 months and then every 2 months thereafter.

o Details of any treatment for SCLC (including surgery) post the last dose of IP must be recorded in the eCRF. At minimum, collect the start date and description of the subsequent anticancer therapy.

Note: All assessments on treatment days are to be performed prior to dosing, unless otherwise indicated.

6.1 Enrollment/screening period

All screening and enrollment procedures will be performed according to the assessment schedule in [Appendix C Table 3 Schedule of assessment for olaparib + ceralasertib \(AZD6738\) combination therapy](#)

. Demographic data and other characteristics will be recorded including date of birth or age, gender, smoking history, and race/ethnicity, according to local regulations. A standard medical and surgical history will be obtained.

Written informed consent and any locally required privacy act document authorization must be obtained prior to performing any protocol specific procedures, including screening/baseline evaluations. Optional informed consent for paired biopsies will also be obtained. If laboratory or imaging procedures were performed for other reasons prior to signing consent, these can be used for screening purposes with consent of the patient. However, all screening laboratory and imaging results must have been obtained within 28 days of enrollment. All patients will have the option to provide consent to supply a sample of their tumor (archived or newly acquired biopsy) for entry into this study. This consent is included in the main patient informed consent form.

Screening/baseline evaluations may be performed over more than 1 visit.

The timing of vital sign assessments should be such that it allows the blood draw (eg, PK blood sample) to occur at the time points indicated in [Appendix C Table 3 Schedule of assessment for olaparib + ceralasertib \(AZD6738\) combination therapy](#)

.

6.2 Treatment period

All procedures to be conducted during the treatment period will be performed according to the assessment schedule (see [Appendix C Table 3 Schedule of assessment for olaparib + ceralasertib \(AZD6738\) combination therapy](#)

).

Whenever vital signs and blood draws are scheduled for the same nominal time, the assessments should occur in the following order: vital signs and then blood draws. The timing of the vital signs assessments should be such that it allows the blood draw (eg, PK blood sample) to occur at the time points indicated in [Appendix C Table 3 Schedule of assessment for olaparib + ceralasertib \(AZD6738\) combination therapy](#)

.

6.3 Follow-up period

All procedures to be conducted during the follow-up period will be performed according to the assessment schedule (see [Appendix C Table 3 Schedule of assessment for olaparib + ceralasertib \(AZD6738\) combination therapy](#)

).

A discontinuation assessment will be performed at the time investigational product is permanently discontinued. In addition patients should be followed up for 30 days after the last dose of study treatment for any new reports of adverse events and other study assessments. Patients should also be asked about concomitant medications at this follow-up. Patients will continue to be followed until disease progression.

7. STUDY ASSESSMENTS

Please also refer to [Section 6](#) of the master protocol for the study assessments applicable to all arms in the study. Additional study assessments applicable to Arm C are listed below.

Prior to discharge from each in-patient and clinic visit, the Investigator or their deputy will be responsible for reviewing all available safety data, including vital signs and ECGs.

7.1.1 Physical examination

A complete physical examination with weight will be performed at the visits as indicated in the study plan and clinically indicated. Height will be recorded at screening only. The following will be assessed: general appearance, respiratory, cardiovascular, abdomen, skin, head and neck (including ears, eyes, nose and throat), lymph nodes, thyroid, abdomen, musculo-skeletal (including spine and extremities) and neurological systems. Clinically relevant worsening of physical examination findings will be recorded as AEs.

Performance status will be assessed at the visits as indicated in the study plan according to US ECOG criteria (see [Section 6.3.1](#) of master protocol for ECOG assessment parameters).

7.1.2 Vital signs

Any changes in vital signs should be recorded as an AE if applicable.

7.1.2.1 Supine blood pressure and pulse rate

Blood pressure and pulse rate will be assessed according to the study plan and as clinically indicated at any other time.

Blood pressure and pulse rate will be measured preferable using a semi-automated BP recording device with an appropriate cuff size after 10 minutes rest.

7.1.2.2 Body temperature

Body temperature will be measured in degrees Celsius at the visits indicated in the study plan.

7.1.3 ECG

Triplicate ECG recordings are required within 7 days prior to starting study treatment (i.e., during screening), as well as at the times as shown in the study plan.

Triplicate ECG recordings should be taken within an approximate 5-minute period. Additional ECGs may be taken at any other time the Investigator deems necessary for safety during the administration period. The patients will rest for at least 10 minutes before the start of each recording and they must be in the same supine body position (maximum 30 degrees flexion in the hip and feet not in contact with the footboard) at the recording time point. The Investigator or designated physician will review the paper copies of each of the timed 12-lead ECGs on each of the study days when they are collected and assess whether they are clinically significantly abnormal/ not clinically significantly abnormal. If there is a clinically significant abnormal finding, the Investigator will record it as an AE on the eCRF. For information on recording of AEs see Section 7.3. The original ECG traces must be stored in the patient medical record as source data.

A standardised ECG machine should be used and the patient should be examined using the same machine throughout the study, where feasible. ECGs will be recorded at 25 mm/sec. Attention should be paid to any detected increases in QTc interval. Patients who develop a single resting value of QTc interval of >450 msec/male and >470 msec/female or a shift from baseline of 60ms should stop taking the study treatment. Dosing can be resumed at a reduced dose after return of the resting QTc interval to pre-treatment status has been confirmed and correction of possible electrolyte imbalance has been made. Monitoring of QTc, checking and correction of abnormal electrolyte levels and renal function are advised, especially in case of severe/prolonged diarrhoea. If QTc increases markedly from baseline, but stays below the above limits, a cardiologist's advice should be sought and Sponsor should be contacted for advice and notification. The concomitant use of ondansetron (known to prolong the QTc interval in rare cases, per labelling) should be taken into account when interpreting QTc changes.

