13. Patient has had prescription or non-prescription drugs or other products known to be sensitive to cytochrome P450 (CYP)3A4 substrates or CYP3A4 substrates with a narrow therapeutic index, or to be moderate to strong inhibitors/inducers of CYP3A4 which cannot be discontinued 2 weeks prior to the first day of study drug dosing and withheld throughout the study until 2 weeks after the last dose of study drug. Coadministration of aprepitant or fosaprepitant during this study is prohibited. The use of sensitive substrates of CYP3A4, such as atorvastatin, simvastatin and lovastatin, is also prohibited in this study. As grapefruit and Seville oranges are known to contain moderate inhibitors of CYP3A4, these fruits or their products (including marmalade, juice, etc.) should be avoided while taking AZD1775. (see Appendix I Disallowed Medications and Medications to be Administered with Caution). Transporter studies (in vitro) have shown that AZD1775 is an inhibitor of breast cancer resistance protein (BRCP). The use of rosuvastatin in this study is prohibited.
14. Herbal preparations are not allowed throughout the study. These herbal medications include but are not limited to: St. John's wort, kava, ephedra (ma hung), ginkgo biloba, dehydroepiandrosterone (DHEA), yohimbe, saw palmetto and ginseng. Patients should stop using these herbal medications 7 days prior to first dose of study treatment.
15. Patients with Grade ≥ 2 neuropathy will be evaluated on a case-by-case basis after consultation with AstraZeneca Study Physician.
16. Patient with mean resting corrected QT interval (specifically QTc calculated using the Fridericia formula) > 470 msec from 3 ECGs performed within 5 minutes apart at study entry or congenital long QT syndrome.
17. Any of the following cardiac diseases currently or within the last 6 months as defined by New York Heart Association \geq Class 2 ([Appendix B1 New York Heart Association Criteria](#))
18.).
 - Unstable angina pectoris
 - Congestive heart failure
 - Acute myocardial infarction
 - Conduction abnormality not controlled with pacemaker or medication
 - Significant ventricular or supraventricular arrhythmias (patients with chronic rate-controlled atrial fibrillation in the absence of other cardiac abnormalities are eligible)
18. AZD1775 should not be given to patients who have a history of Torsades de pointes unless all risk factors that contributed to Torsades have been corrected (see Section

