6.1.2 ECG

A 12-lead safety ECG (paper ECG printout of 10 seconds for Investigator review) will be taken at screening and prior to dosing on day 1 of each study cycle.

Triplicate ECG recordings should be taken within an approximate 5-minute period. Additional ECGs may be taken at any other time the Investigator deems necessary for safety during the administration period. The patients will rest for at least 10 minutes before the start of each recording and they must be in the same supine body position (maximum 30 degrees flexion in the hip and feet not in contact with the footboard) at the recording time point.

The Investigator will judge the overall interpretation as normal or abnormal. If abnormal, it will be decided as to whether or not the abnormality is clinically significant or not clinically significant. The paper copy of each ECG reading will be retained with the patient’s completed source documents. Only overall evaluation (normal/abnormal) will be recorded in the eCRF. If there is a clinically significant abnormal unscheduled ECG finding during the treatment

period, this should be recorded on the AE eCRF, according to standard AE collection and reporting processes (see Section 7).

Attention should be paid to any detected increases in QTc interval. Patients who develop a single resting value of QTc interval of >450 msec/male and >470 msec/female or a shift from baseline of ≥ 60 ms should stop taking AZD1775. Dosing can be resumed at a reduced dose after return of the resting QTc interval to pre-treatment status has been confirmed and correction of possible electrolyte imbalance has been made (see [Appendix B Table](#)).

Monitoring of QTc, checking and correction of abnormal electrolyte levels and renal function are advised, especially in case of severe/prolonged diarrhoea. If QTc increases markedly from baseline, but stays below the above limits, a cardiologist’s advice should be sought.

The concomitant use of ondansetron (known to prolong the QTc interval in rare cases, per labelling) should be taken into account when interpreting QTc changes.

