7.3.2 Dose modifications due to non-hematologic related adverse events

Dose modifications for non-hematologic toxicities should be based on toxicities occurring during the previous cycle. For toxicities that lead to a dose reduction, the dose will not be re-escalated during subsequent cycles.

Any patient who develops a Grade 3 or 4 non-hematologic toxicity that does not resolve to \leq Grade 1 within 28 days should be discontinued from the study treatment. However, if the Investigator determines that the non-hematologic toxicity was due to one study drug and not the other, treatment with the remaining study drug may continue as clinically appropriate.

Based upon the maximum non-hematologic toxicities experienced during the previous cycle, dose adjustments for subsequent cycles are to be made according to the criteria defined in [Appendix B Table 9](#) (unless specified per unique toxicities as noted below).

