Appendix B Table 9 Non-hematologic toxicity dose modification and management

Electrocardiogram QT corrected interval prolonged		
QTc Value	CBDP	AZD1775
QTc 450-480 ms (males) or 470-480 (females)	No dose modifications	Hold. Once QTc interval has returned to pretreatment status and correction of possible electrolyte imbalance has been made, resume at next lower dose level.
QTc 481-500 ms	No dose modifications	Hold. Seek cardiologist advice.

QTc \geq 501 ms	Discontinue treatment	Discontinue treatment
Shift from baseline of \geq 60ms	Discontinue treatment	Discontinue treatment
<hr/>		
CTCAE version 4.03	CBDP	AZD1775
Grade 0 - 2	No dose modification	No dose modification
Grade 3 ^{b,c,d}	Hold ^a	Hold ^a
Grade 4 ^b	Hold until toxicity resolves to Grade \leq 1. Resume with 1 dose level reduction	Hold until toxicity resolves to Grade \leq 1. Resume with 1 dose level reduction
Second repeat incidence of Grade 3 or 4 toxicity (except nausea, vomiting, fatigue, malaise, lethargy, anorexia, alopecia)	Discontinue treatment	Discontinue treatment
<hr/>		
Hepatic		
<hr/>		
CTCAE v4.03	CBDP	AZD1775
Grade 1-2	No dose modification	No dose modification
Grade 3 or 4 (manifested as elevations in ALT, AST, ALP, or bilirubin)	Hold until resolves to Grade \leq 1 or baseline, then resume CBDP with a 1 level dose reduction. If not resolved within 28 days, discontinue CBDP.	Hold until resolves to Grade \leq 1 or baseline, then resume study drug with a 1 level dose reduction. If not resolved within 28 days, discontinue study drug.
<hr/>		
Diarrhea or mucositis		
<hr/>		
CTCAE v4.03	CBDP	AZD1775
Grade 1-2	No dose modification	No dose modification
Grade 3 or 4 (or requiring hospitalization)	Hold ^a	Hold ^a
<hr/>		
Nephrotoxicity		
<hr/>		
CTCAE v4.03	CBDP	AZD1775
Grade 0-1	No dose modification	No dose modification

Grade ≥ 2 Hold until resolves to Grade ≤ 1 or Hold^a
baseline, then resume CBDP with
a 1 level dose reduction. If not
resolved within 28 days,
discontinue CBDP.

Neurotoxicity		
CTCAE v4.03	CBDP	AZD1775
Grade 1	No dose modification	No dose modification
Grade 2	Hold until toxicity resolves to Grade ≤ 1 . Resume with 1 dose level reduction.	No dose modification
Grade 3 or 4	Discontinue treatment	Discontinue treatment

- ^a Hold until toxicity resolves to \leq Grade 1 and then resume at the same dose with no modification.
- ^b Dose reduction for nausea and vomiting should be made only if Grade 3 or Grade 4 toxicity occurs in spite of maximum anti-emetics.

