7.3.3.6 QTc prolongation

The QTc interval will be measured in 12-lead ECGs at baseline and at the commencement of each treatment cycle; and an assessment made of the emergence, if any, of QTc prolongation. Serum electrolyte levels should be obtained at baseline and at commencement of each treatment cycle.

Checking and correction of abnormal electrolyte levels and renal function are advised, especially in case of diarrhoea.

The administration of AZD1775 with substances known to prolong the ECG QTc interval is not recommended.

Special note: The potential risk of concomitant use of AZD1775 with ondansetron (known to prolong the QTc interval) should be taken into account.

Dose modifications or discontinuations for patients experiencing QTc prolongations are summarized in [Appendix B Table](#) above.

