19. Cardiac dysfunction as defined as: Myocardial infarction within six months of study entry, NYHA Class II/III/IV heart failure, unstable angina, unstable cardiac arrhythmias or known reduced LVEF $< 55\%$
20. Any of the following cardiac criteria:

- Mean resting corrected QT interval (QTc) >470 msec obtained from 3 electrocardiograms (ECGs) in 24 hours using the Fredericia formula
 - Any clinically important abnormalities in rhythm, conduction or morphology of resting ECG (e.g., complete left bundle branch block, third degree heart block)
 - Any factors that increase the risk of QTc prolongation or risk of arrhythmic events such as heart failure, hypokalaemia, congenital long QT syndrome, immediate family history of long QT syndrome or unexplained sudden death under 40 years of age
 - Patients at risk of brain perfusion problems, e.g., carotid stenosis
 - Patients with relative hypotension (< 100/60 mm Hg) or clinically relevant orthostatic hypotension, including a fall in blood pressure of >20mm Hg
 - Uncontrolled hypertension requiring clinical intervention
21. Refractory nausea and vomiting, chronic gastrointestinal diseases or previous significant bowel resection, with clinically significant sequelae that would preclude adequate absorption of ceralasertib or olaparib.
22. Patients with uncontrolled seizures.
23. Judgment by the Investigator that the patient should not participate in the study if the patient is unlikely to comply with study procedures, restrictions and requirements.
24. Radiation therapy to the chest and whole-brain irradiation must be completed at least 4 weeks prior to start of study treatment, and patients must have recovered from any acute adverse effects prior to start of study treatment. An exception to this is palliative radiotherapy with a limited field of radiation for palliation, which must be completed before the first dose of study treatment. In the case of palliative radiation to more than 30% of the bone marrow or with a wide field of radiation this must also be completed at least 4 weeks prior to the first dose of study medication.
25. Intestinal obstruction or CTCAE grade 3 or grade 4 upper GI bleeding within 4 weeks before the dosing.
26. Patients with myelodysplastic syndrome/acute myeloid leukaemia or with features suggestive of MDS/AML.

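### Arm B gives two different instructions for a QTc shift of 60 ms or more, and Arms B and C admit men up to a QTcF of 470 ms but stop them above 450 ms

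*Protocol*

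**What the plan says.** **Entry.** Arm B (Appendix B section 4.2, criterion 16) excludes a patient with "mean resting corrected QT interval (specifically QTc calculated using the Fridericia formula) > 470 msec from 3 ECGs". Arm C (Appendix C section 5.2, criterion 20) excludes "Mean resting corrected QT interval (QTc) >470 msec obtained from 3 electrocardiograms (ECGs) in 24 hours using the Fredericia formula". Neither criterion sets a separate limit for men.

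**On treatment.** Appendix B section 6.1.2 and Appendix C section 7.1.3 use the same trigger, "a single resting value of QTc interval of >450 msec/male and >470 msec/female", and add a 60 ms shift from baseline as an alternative. In Arm B such patients "should stop taking AZD1775. Dosing can be resumed at a reduced dose" once QTc is back to its pre-treatment status and electrolytes are corrected. Arm C stops study treatment on the same terms.

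**Arm B Table 9.** The first QTc row covers 450-480 ms in men and 470-480 ms in women: hold AZD1775, then resume one dose level lower, with no carboplatin change. A separate row for a shift of 60 ms or more discontinues both AZD1775 and carboplatin. Appendix B section 7.3.3.6 refers to an Appendix B table for QTc dose modifications and discontinuations.

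**The concern.** There are two separate faults.

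1. In Arm B, section 6.1.2 allows restart after a 60 ms shift and Table 9 does not. A site that follows the ECG section would resume AZD1775. A site that follows the table would end both drugs.

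2. In Arms B and C, a man with a mean QTcF above 450 ms and up to 470 ms is eligible, yet already sits over the on-treatment limit for his sex. Nothing says what to do if his QTc simply stays where it was. Applied to the letter, the rule holds his drug and lowers his dose without any drug effect on QTc. Sites that read the rule differently would dose the same man differently.

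**Working it through.** No plan figure needs to be reproduced. The check compares sections and adds simple dose arithmetic. I take QTc in the stop rules to be Fridericia-corrected, as at entry; the stop rules do not name the correction.

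**The 60 ms shift in Arm B.** Take a hypothetical woman with baseline QTc 400 ms and an on-treatment reading of 465 ms.
- Shift: 465 - 400 = 65 ms, so the shift rule applies. Her reading is below 470 ms, so no absolute limit applies.
- Section 6.1.2: stop AZD1775; restart at a reduced dose is possible once QTc has returned. Carboplatin is not mentioned.
- Table 9: discontinue AZD1775 and carboplatin.

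The conflict needs no assumption and affects both sexes. Arm C has no equivalent: section 7.1.3 allows restart after a shift, and I find no QTc rule in section 8.4 that says otherwise.

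**Entry against stop limit, Arms B and C.**
- Women: admitted up to 470 ms, stopped above 470 ms. The limits agree, apart from a reading of exactly 470 ms in Table 9.
- Men: admitted up to 470 ms, stopped above 450 ms. The limits overlap above 450 ms and up to 470 ms.

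Take a man with baseline 460 ms and a later reading of 460 ms. His shift is 0 ms. He is over 450 ms, so the stop applies as written. He is already at his pre-treatment status, so the restart condition is met at once. The rule's only effect is a hold and a lower dose.

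**Size of one dose step** (Appendix B Table 6; Appendix C Table 5, non-haematological row):
- AZD1775: 5 x 225 = 1125 mg to 5 x 175 = 875 mg per cycle; 250/1125 = 22%.
- Ceralasertib: 7 x 160 = 1120 mg to 7 x 120 = 840 mg per cycle; 280/1120 = 25%.
- Olaparib: 300 to 250 mg twice daily; 50/300 = 17%.

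Section 7.1.3 does not say which Arm C drug to reduce. Table 5 allows either or both. Appendix B section 7.3.2 and Appendix C section 8.4.1 bar re-escalation, so a reduction would be permanent.

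**How many men.** The protocol gives no baseline QTc distribution and no sex mix. As an assumption only, let male QTcF be normal with mean 405-425 ms and SD 15-25 ms, with F its distribution function. The share of eligible men in the gap is [F(470) - F(450)]/F(470):
- Lowest (mean 405, SD 15): 0.13%.
- Central (mean 415, SD 20): 3.7%.
- Highest (mean 425, SD 25): 12.7%.

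Appendices B and C plan up to 20 patients per arm. If 50-100% are men (10 to 20 men), the expected number runs from 10 x 0.0013 = 0.01 to 20 x 0.1273 = 2.5 per arm. The central value is 10 x 0.0372 = 0.4 to 20 x 0.0372 = 0.7. An expansion to 40, which the master protocol allows, would double these. The range is wide because it rests entirely on assumed inputs. Arm C's further QT-risk exclusions in criterion 20 would lower it.

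**The case against.** The best reply to the 450/470 ms gap is that the rule is about new prolongation. Both ECG sections introduce it by speaking of *detected increases* and apply it to patients who *develop* the value. Return to pre-treatment status presupposes a departure from it. Appendix B section 7.3.3.6 calls for "an assessment made of the emergence, if any, of QTc prolongation", and section 7.3.2 says "Dose modifications for non-hematologic toxicities should be based on toxicities occurring during the previous cycle". This probably is the intent, and it is why the fault is minor. It does not close the gap. The Table 9 row is a plain absolute band with no reference to baseline, change from baseline has its own 60 ms criterion, and no sentence exempts an unchanged value.

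On the 60 ms shift, the restart sentence in section 6.1.2 is permissive and cross-refers to an Appendix B table, and section 7.3.3.6 points to a table as well. Table 9 is therefore very likely meant to govern. That shows how to resolve the conflict but does not remove it from the text.

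Two stronger readings are tempting and are not supported.

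- A reader might infer that the QTc rule is harsher than the rule for a first severe toxicity, because some first Grade 3 events restart at full dose. Others do not. In Arm B, the hepatic and general Grade 4 rows of Table 9 cut one level at a first event, and Table 8 lowers AZD1775 after a first Grade 3 neutropenia or thrombocytopenia. In Arm C, Table 7 lowers olaparib after Grade 3 anaemia.
- A reader might infer that drug is stopped on one unconfirmed reading and that the stop should rest on a triplicate mean. Master protocol section 6.2.3 already asks for two further ECGs to confirm a clinically significant abnormality. Its named triggers are QTcF above 470 ms or a 60 ms shift, so at 451-470 ms confirmation depends on the investigator's judgement. Both arms also state "Triplicate ECG recordings should be taken within an approximate 5-minute period". Moving a safety stop from a single reading to a mean would loosen it. That is a trade-off and not the correction of an error.

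**Conclusion.** The protocol is wrong as written on both counts, and both are minor. The Arm B conflict over a shift of 60 ms or more is certain on the text. The gap for men in Arms B and C is also on the text, but its consequence depends on a literal reading that the surrounding wording does not favour.

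Under that reading, one trigger costs a man 22% of AZD1775 per cycle in Arm B, or 25% of ceralasertib and/or 17% of olaparib in Arm C. How many men this concerns is not knowable from the protocol; under the assumptions above the central expectation is below one per 20-patient arm. A reader might infer that lost dose bears on the response rate. Nothing in the documents supports that, and it is not claimed. A stop limit stricter than the entry limit is not in itself an error; the fault is that nothing says how to handle men admitted between the two.

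**What to change.** 1. **Arm B, 60 ms shift.** Amend Appendix B section 6.1.2 so that the restart sentence does not apply to a shift of 60 ms or more, and state that Table 9 governs.

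2. **Men at 451-470 ms, Arms B and C.** Choose one:
   - Exclude men with a mean triplicate QTcF above 450 ms (Appendix B criterion 16, Appendix C criterion 20). The cost is a few men lost at screening. Three ECGs are already required there.
   - Leave eligibility unchanged. State in Appendix B section 6.1.2, Table 9 and Appendix C section 7.1.3 that the 450 ms male limit applies only to values newly above 450 ms relative to baseline, and that men who entered at 451-470 ms stop at above 470 ms or at a 60 ms shift. For these men a 60 ms shift means at least 451 + 60 = 511 ms, so 470 ms is the limit that acts in practice.

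Either choice is a wording change in two appendices with no additional scheduled ECG visits. The second loses no eligible patients. The first is simpler for sites to apply.
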